### **5.2.2 Daunorubicin**

1) Content and dosage form: Red lyophilized formulation (pH 5.0 to 6.5) that contains 20 mg of daunorubicin hydrochloride and 100 mg of D-Mannitol as an inactive ingredient per vial.

### **5.2.3 Idarubicin**

1) Content and dosage form: Yellow-red lyophilized formulation (pH 5.0 to 7.0) that contains 5 mg of idarubicin hydrochloride and 50 mg of lactose hydrate as an inactive ingredient per vial.

## **5.3 Treatment Method of the Study Drug and Coadministered Drugs (Cytarabine and Anthracycline Drugs)**

### **5.3.1 Dose and Regimen**

Quizartinib will be orally administered at the dose listed below once daily every morning under fasting conditions (at least 1 hour before or at least 2 hours after breakfast).

Table 5.3-1 Quizartinib Dose

Level	Dose
1	20 mg
2	40 mg

If a patient vomits after taking a dose of quizartinib, a replacement dose may not be given on the same day. A patient who did not take quizartinib at the usual hour of dosing (eg,

forgot to take the dose) will be allowed to take the missed dose at least 1 hour before or at least 2 hours after a meal within about 10 hours after the usual hour of dosing (for example, if the patient usually takes the drug at 7:00 or 8:00, he/she may take it until around 18:00). A patient who did not take the missed dose within about 10 hours after the usual hour of dosing should not take quizartinib on that day, and resume taking quizartinib on the following day. The patient may not take two doses at once on the day when the drug is resumed.

Remission induction therapy and consolidation therapy will be given for up to 2 cycles and 4 cycles, respectively, each of which is 28 days long.

### **Remission Induction Therapy**

- \* As an anthracycline drug, either daunorubicin or idarubicin will be chosen, and the same drug will be used in Cycle 1 and Cycle 2.

#### Cycle 1 (“7 + 3”)

- Cytarabine: Cytarabine, which is diluted with 5% glucose solution or 5% normal saline to make a total volume of 250 mL to 500 mL, will be administered at a daily dose of  $100 \text{ mg/m}^2$  by 24-hour continuous intravenous infusion for 7 consecutive days on Day 1 to Day 7.
- Daunorubicin: Daunorubicin, which is dissolved in 10 mL of Japanese Pharmacopoeia (JP) sterile water for injection per vial, will be administered at a daily dose of  $60 \text{ mg/m}^2$  by intravenous infusion over a period of 30 to 60 minutes on Day 1 to Day 3.
- Idarubicin: Idarubicin, which is dissolved in 5 mL of JP sterile water for injection per vial, will be administered at a daily dose of  $12 \text{ mg/m}^2$  by intravenous infusion over a period of 30 to 60 minutes on Day 1 to Day 3.
- Quizartinib: After the end of cytarabine administration, quizartinib will be orally administered at a dose of 20 mg or 40 mg once daily on Day 8 to Day 21.

#### Cycle 2

- \* The treatment will be administered using the same regimen as in Cycle 1 (“7 + 3”) or as shown below (“5 + 2”).
- Cytarabine: Cytarabine, which is diluted with 5% glucose solution or 5% normal saline to make a total volume of 250 mL to 500 mL, will be

[figure not shown]
administered at a daily dose of  $100 \text{ mg/m}^2$  by 24-hour continuous intravenous infusion for 5 consecutive days on Day 1 to Day 5.

- Daunorubicin: Daunorubicin, which is dissolved in 10 mL of JP sterile water for injection per vial, will be administered at a daily dose of  $60 \text{ mg/m}^2$  by intravenous infusion over a period of 30 to 60 minutes on Day 1 to Day 2.
- Idarubicin: Idarubicin, which is dissolved in 5 mL of JP sterile water for injection per vial, will be administered at a daily dose of  $12 \text{ mg/m}^2$  by intravenous infusion over a period of 30 to 60 minutes on Day 1 to Day 2.
- Quizartinib: After the end of cytarabine administration, quizartinib will be orally administered at a dose of 20 mg or 40 mg once daily on Day 6 to Day 19.

### **Consolidation Therapy**

- Cytarabine: Cytarabine, which is diluted with 5% glucose solution or 5% normal saline to make a total volume of 300 mL to 500 mL, will be administered at a dose of  $3.0 \text{ g/m}^2$  for patients of < 60 years old or  $1.5 \text{ g/m}^2$  for patients of  $\geq 60$  years old (age at the time of registration in the study) by intravenous infusion over a period of 3 hours a total of 6 times every 12 hours on Day 1, Day 3, and Day 5.
- Quizartinib: After the end of the 6th dose of cytarabine, quizartinib will be orally administered at a dose of 20 mg or 40 mg on Day 6 to Day 19.

Figure 5.3-1 Summary of Study Treatment Schedule

**<Rationale>**

Refer to “1.5 Rationale for the Dosage.”

**5.3.2 Emergency Procedures and Management in the Event of Quizartinib Overdose**

In the event of overdose of quizartinib, the investigator or subinvestigator should immediately assess the patient's condition, and if any symptoms are found, immediately provide appropriate intervention and supportive therapy. The investigator and sponsor will discuss and decide whether the patient may continue study participation or not, taking the status of overdose and the subsequent course of the patient into consideration. For overdose occurring during the DLT assessment period, the patient will be excluded from the DLT assessment (refer to “5.4.4 Enrollment of Additional Patients”).

In an overseas Phase 1 study (Study CP0001), quizartinib was tested with treatment cycles of intermittent dosing (14 days on the drug followed by 14 days of rest) at 450 mg/day, and 28-day continuous dosing at 200 and 300 mg/day. No DLTs occurred in 6 patients receiving intermittent dosing at 450 mg/day, whereas Grade 3 QTc

prolongation was seen in 1 of 17 patients on continuous dosing at 200 mg/day and in 3 of 8 patients on continuous dosing at 300 mg/day.

### **5.3.3 Emergency Procedures and Management in the Event of Cytarabine and Anthracycline Overdoses**

In the event of overdose of cytarabine or an anthracycline drug, the investigator or subinvestigator should immediately assess the patient's condition, and if any symptoms are found, immediately provide appropriate intervention and supportive therapy. The investigator and sponsor will discuss and decide whether the patient may continue study participation or not, taking the status of overdose and the subsequent course of the patient into consideration.

### **5.3.4 Randomization and Blinding**

Neither randomization or blinding will be used in the study.

## **5.4 Assessment of Dose-limiting Toxicity**

### **5.4.1 Definition of Dose-limiting Toxicities**

The DLT assessment period is from the start day of quizartinib administration in Cycle 1 of remission induction therapy to the preceding day of Day 1 of Cycle 1 of consolidation therapy (induction phase), and a DLT is defined as any toxicity among AEs that occur during the above period that are assessed to be “related” to quizartinib, as listed below. The severity grade will be assessed according to the Common Terminology Criteria for Adverse Events (CTCAE) v4.0 Japanese version.

- $\geq$  Grade 3 non-hematological toxicities (except for the following)
  - Alopecia, anorexia, and fatigue
  - Grade 3 queasy, vomiting, or diarrhea that has improved to  $\leq$  Grade 2 within 7 days after the onset after treatment with antiemetic or antidiarrheal drugs
  - Grade 3 mucositis that has improved to  $\leq$  Grade 2 within 7 days after the onset
  - Grade 3 infections
  - Febrile neutropenia
- Hematological toxicities that have not resolved before Day 1 of Cycle 1 of consolidation therapy, as listed below
  - Peripheral neutropenia ( $< 500/\text{mm}^3$ )
  - Thrombocytopenia resulting from bone marrow aplasia or hypoplasia ( $< 20\,000/\text{mm}^3$ )

- $\geq$  Grade 3 thrombocytopenia associated with bleeding ( $< 50\ 000/\text{mm}^3$ )
- Grade 4 thrombocytopenia requiring blood transfusion ( $< 25\ 000/\text{mm}^3$ )

If there is a day when quizartinib cannot be taken due to any toxicity during the DLT assessment period, the investigator and the sponsor will discuss and decide whether to handle the toxicity as a DLT or not.

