#### 5.4.2 Assessment Method of Dose-limiting Toxicity

Quizartinib will be administered at a dose of 20 mg at Level 1 and 40 mg at Level 2. Dose escalation within a single patient is not allowed. For the dose of cytarabine and the anthracycline drug used for remission induction therapy, refer to Section “5.3.1 Dose and Regimen.”

DLT assessment at each level will first be conducted in 3 patients (including at least 1 patient of  $< 60$  years old at the time of registration in the study). DLT assessment for each patient will basically be conducted after the end of the DLT assessment period for the patient; however, if both the investigator and the sponsor decide it necessary to terminate the patient’s participation in the study, eg,  $\geq$  Grade 3 non-hematological toxicity occurs during the DLT assessment period and is assessed to be “related” to quizartinib, and premature termination of the study is considered necessary to ensure the patient’s safety, it is allowed to assess DLTs before the end of the DLT assessment period. If DLTs do not occur in the first 3 patients at Level 1, the treatment will proceed to Level 2. If DLTs occur in the first 3 patients at Level 1, an additional 3 patients will be enrolled at Level 1 or quizartinib dose escalation will be discontinued in accordance with “Table 5.4-1 Criteria for Proceeding to Level 2.” If the treatment proceeds to Level 2, the MTD will be determined in accordance with “Table 5.4-2 Criteria for Assessing Maximum Tolerated Doses (MTDs) at Level 2.”

Table 5.4-1 Criteria for Proceeding to Level 2

Incidence of DLTs in the first 3 patients at Level 1, and the decision	Incidence of DLTs when 3 patients are additionally enrolled at Level 1 (a total of 6 patients), and the decision
0 of 3 patients: Proceed to Level 2.	—
1 of 3 patients: Additionally enroll 3 patients at Level 1.	1 of 6 patients or 2 of 6 patients: Proceed to Level 2. 3 of 6 patients or 4 of 6 patients: Stop increasing the dose of quizartinib (study termination).
2 of 3 patients or 3 of 3 patients: Stop increasing the dose of quizartinib (study termination).	—

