**Table 5.4-2 Criteria for Assessing Maximum Tolerated Doses (MTDs) at Level 2**

Incidence of DLTs in the first 3 patients at Level 2, and the decision	Incidence of DLTs when 3 patients are additionally enrolled at Level 2 (a total of 6 patients), and the decision
0 of 3 patients: Terminate the study (MTD: 40 mg).	—
1 of 3 patients: Additionally enroll 3 patients at Level 2.	1 of 6 patients or 2 of 6 patients: Terminate the study (MTD: 40 mg). 3 of 6 patients or 4 of 6 patients: Terminate the study (MTD: 20 mg).
2 of 3 patients or 3 of 3 patients: Terminate the study (MTD: 20 mg).	—

If any of the criteria provided in “5.4.4 Enrollment of Additional Patients” is met at Level 1 and any patient is excluded from DLT assessment, information on AEs occurring in the concerned patient, etc. should be taken into consideration to assess whether to proceed to Level 2 or not.

Whether it is necessary or not to establish a new level, in addition to Level 1 and Level 2, will be determined through discussion between the investigator and the sponsor. The medical expert will be consulted as needed.

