#### **5.4.4 Enrollment of Additional Patients**

If any of the following apply, the need to enroll additional patients at the level or not will be determined through discussion between the investigator and the sponsor. The medical expert will be consulted as needed. If enrollment of additional patients is determined, the patients meeting any of the following will be excluded from DLT assessment.

- A patient is found to be ineligible after registration.
- A patient has taken quizartinib for the following number of days during the DLT assessment period.
  - The number of days of quizartinib administration is  $\leq 9$  for patients who have completed remission induction therapy in Cycle 1
  - The number of days of quizartinib administration is  $\leq 9$  both in Cycle 1 and Cycle 2 for patients who have proceeded to remission induction therapy in Cycle 2.
- A patient takes quizartinib at a higher dose at once than the dose given at the participating level during the DLT assessment period.

- The investigator or the sponsor considers it difficult to assess DLTs in a patient because some procedures during the DLT assessment period have not been performed appropriately.
- A patient is withdrawn from the study because the patient meets the criteria specified in “5.6 Withdrawal Criteria” during the DLT assessment period (except in case the study is terminated due to DLTs).
- Enrollment of additional patients is otherwise considered necessary for safety evaluation.

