#### **11.1.3 MTD Analysis Set**

The MTD Analysis Set is defined as patients who received at least 1 dose of any of the study drug, cytarabine, and the anthracycline drug, but excludes the patients listed below.

- Patients whose DLT assessment has not been performed appropriately because some of the procedures during the DLT assessment period are missing for other reasons than adverse drug reactions (eg, worsening of the clinical condition due to progression of the primary disease, AEs that are assessed as not related to the study drug)
- Patients who have taken quizartinib for the following number of days during the DLT assessment period
  - The number of days of quizartinib administration is  $\leq 9$  for patients who have

completed remission induction therapy in Cycle 1

- The number of days of quizartinib administration is  $\leq 9$  both in Cycle 1 and Cycle 2 for patients who have proceeded to remission induction therapy in Cycle 2.

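### The hematological DLT item is judged at the start of consolidation, a day the visible text neither fixes nor limits and some patients may never reach

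*Combined protocol and SAP*

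**What the plan says.** Section 5.4.1 opens the DLT window on the first quizartinib day of induction Cycle 1 (Day 8) and runs it "to the preceding day of Day 1 of Cycle 1 of consolidation therapy (induction phase". Non-hematological toxicities are graded events within that window. The hematological item covers low neutrophil and platelet counts and is tied to one day: "Hematological toxicities that have not resolved before Day 1 of Cycle 1 of consolidation therapy, as listed below". All DLTs must be judged related to quizartinib.

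On timing, section 5.3.1 gives 28-day cycles. Section 6.2 lets induction Cycle 2 start up to 56 days after Day 1 of Cycle 1. Section 6.3 gives the same +56-day allowance for consolidation Cycle 2 and later. For consolidation Cycle 1 the only stated condition is fewer than 5% myeloblasts on Day 21 (section 6.2).

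On who is assessed and when:

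- Section 5.4.2: "DLT assessment for each patient will basically be conducted after the end of the DLT assessment period for the patient". Earlier assessment is allowed if the investigator and sponsor agree that participation must end.
- Section 5.4.1: if a toxicity prevents a quizartinib dose, "the investigator and the sponsor will discuss and decide whether to handle the toxicity as a DLT or not".
- Section 5.4.4: a patient withdrawn during the window may be excluded and replaced, "except in case the study is terminated due to DLTs".
- Section 11.1.3: the MTD Analysis Set drops patients with 9 or fewer quizartinib days, and those not properly assessed because "some of the procedures during the DLT assessment period are missing for other reasons than adverse drug reactions".

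**The concern.** The 3 + 3 count decides escalation and the MTD, and so serves the primary objective of choosing a dose. The hematological item is meant to catch slow marrow recovery, but the date it is judged against can depend on that recovery. If consolidation is held until counts return, every patient who eventually recovers escapes the item, whether recovery took days or weeks. Elsewhere in the same list, gastrointestinal events and mucositis have a fixed 7-day rule; the hematological item has no fixed time.

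The second gap is a missing date. Withdrawal during the window is foreseen in sections 5.4.4 and 5.6, and the visible text gives no path to consolidation for a patient with 5% or more blasts after induction Cycle 2. For a patient who never starts consolidation, Day 1 of consolidation does not exist. The exception in 5.4.4 for participation ended by DLTs then rests on a judgment with no defined day.

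**Working it through.** **1. The plan's own figure.** Two levels of 3 to 6 patients give 2 × 3 = 6 to 2 × 6 = 12, which matches section 11.5. The concern does not affect it.

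**2. Window length from the stated rules** (induction Cycle 1 Day 1 = study Day 1, counted inclusively from Day 8).

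- One induction cycle, consolidation on Day 29: 28 − 8 + 1 = 21 days.
- Two cycles, no delay: 56 − 8 + 1 = 49 days.
- Cycle 2 at its limit, Day 1 + 56 = Day 57, ending Day 84: 84 − 8 + 1 = 77 days.

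Any wait before consolidation Cycle 1 comes on top, and the visible text says nothing about its length.

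**3. The same event under two start dates.** Take related neutrophils below 500/mm³ through Day 40, resolved on Day 41. If consolidation starts on Day 40, the cytopenia is unresolved and is a DLT. If it starts on Day 42, the cytopenia resolved first and is not a DLT.

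**4. Effect of one patient on the decision** (Tables 5.4-1 and 5.4-2).

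| Count | One fewer | Level 1 decision | Level 2 decision |
|---|---|---|---|
| 1/3 | 0/3 | enroll 3 more → proceed | enroll 3 more → MTD 40 mg |
| 2/3 | 1/3 | stop → enroll 3 more | MTD 20 mg → enroll 3 more |
| 3/6 | 2/6 | stop → proceed | MTD 20 mg → MTD 40 mg |

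The last row applies when the reclassified patient is among the second three.

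**5. Illustration on assumed rates only.** Let q be the non-hematological DLT rate, h the rate of prolonged related cytopenia that a dated rule would count, and k the share of it counted, with independence. The counted rate is p = 1 − (1 − q)(1 − hk). A level passes with 0/3, or with 1/3 and then at most one DLT in the next three:

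Pass(p) = (1 − p)³ + 3p(1 − p)² × [(1 − p)³ + 3p(1 − p)²].

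Example: q = 10%, h = 20%, k = 1 gives p = 0.28 and 0.373 + 0.435 × 0.809 = 0.725. With k = 0.5, p = 0.19 and the result is 0.531 + 0.374 × 0.905 = 0.870.

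| q | h | Pass, all counted | Pass, half counted |
|---|---|---|---|
| 10% | 10% | 87% | 93% |
| 10% | 20% | 73% | 87% |
| 10% | 30% | 55% | 80% |
| 20% | 10% | 73% | 79% |
| 20% | 20% | 57% | 73% |
| 20% | 30% | 42% | 65% |

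None of q, h or k comes from the documents. The table shows how sensitive the rule is; it does not estimate this trial.

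**6. Sections 5.4.4 and 11.1.3 side by side.** Take a patient with more than 9 quizartinib days and all induction procedures done who withdraws consent before consolidation. Section 5.4.4 allows exclusion and replacement. Section 11.1.3 does not exclude this patient, because no procedure is missing. Many withdrawals for "worsening of the clinical condition due to progression of the primary disease, AEs that are assessed as not related to the study drug" are already covered there, so the mismatch is narrow.

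**The case against.** A reader might infer that consolidation may be delayed without limit. The documents do not establish that. Postponement is granted expressly for induction Cycle 2 and for later consolidation cycles, and not for consolidation Cycle 1. Read strictly, with 28-day cycles, no delay is allowed and the moving-date problem disappears. The two unseen figures may also carry a limit. This part stands: the text is silent, and silence supports either reading.

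A reader might also say that DLTs are being missed. A cytopenia that clears before consolidation is not a DLT by the protocol's own definition, and judging recovery at the next treatment phase is a legitimate choice. The criticism is only that the yardstick can move with the event it measures.

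Declining the second consent in section 15.3 is a tempting route to a missing assessment, but a weak one. That consent concerns participation after the DLT window, so refusing it does not show that the assessment was prevented.

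Some cover exists. Laboratory tests are scheduled before cytarabine on consolidation Cycle 1 Day 1 (section 6.3), at withdrawal (6.4) and 28 days after the last dose (6.5). Section 5.4.4 allows replacement, and section 11.1 lets the sponsor settle population flags for unspecified cases. In 6 to 12 patients, case-by-case judgment is workable. But replacement and flagging are discretionary, and the 6.4 and 6.5 counts are not tied to the DLT definition. The missed-dose clause need not be triggered by a cytopenia that persists after the last scheduled dose. Review of AEs in excluded patients applies when a criterion "is met at Level 1 and any patient is excluded from DLT assessment, information on AEs occurring in the concerned patient", so it names Level 1 only, although Table 5.4-2 sets the MTD at Level 2.

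Finally, the delayed neutrophil and platelet recovery in sections 1.3.2 and 1.4 came from continued dosing in relapsed or refractory disease. It makes the risk plausible here and does not measure it.

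**Conclusion.** The point holds in a limited form. As written, the hematological item depends on a day that the visible text neither fixes nor limits, and that day does not exist for a patient who never starts consolidation. The first gap is conditional on the start being postponable; the second does not depend on that. One reclassified patient is enough to change escalation or the MTD. How often this would happen cannot be derived from the documents, and the pass probabilities above rest wholly on assumed rates. The DLT count is also not the only safeguard: TEAEs are tabulated by grade, and section 3 says consolidation-phase safety data will inform the decision on joining the global study. Severity is moderate to minor.

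**What to change.** Leave unchanged the DLT window for non-hematological events, the count thresholds and the relatedness requirement. Ending the whole window earlier would lose related non-hematological events that 5.4.1 now counts.

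For the hematological item only:

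- Judge it at the earlier of consolidation Cycle 1 Day 1, using the pre-cytarabine laboratory test already scheduled, and a latest day pre-specified by the sponsor and counted from Day 1 of the last induction cycle.
- Judge a patient who does not start consolidation on that latest day. State in advance which counts are usable; a low count at an early withdrawal visit should not settle the item alone.
- Treat a patient with no other DLT and no usable count by then as not evaluable for this item, in the same way in 5.4.4 and 11.1.3.
- Count a patient who meets the criterion, and do not replace that patient.

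If a figure already gives a latest start for consolidation Cycle 1, or if no postponement is intended, state that in 5.4.1 and reconcile the sections.

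The cost is a few lines in 5.4.1, 5.4.2, 5.4.4 and 11.1.3, and possibly one extra blood count. Scheduled induction laboratory tests end at Day 28. The section 6.5 visit falls near Day 21 + 28 = 49 of the last cycle after 7 + 3 (range 42 to 56), or Day 19 + 28 = 47 after 5 + 2 (range 40 to 54), and earlier if quizartinib stops early. There may be more DLTs, or more patients to replace.

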#### 5.4.2 Assessment Method of Dose-limiting Toxicity

Quizartinib will be administered at a dose of 20 mg at Level 1 and 40 mg at Level 2. Dose escalation within a single patient is not allowed. For the dose of cytarabine and the anthracycline drug used for remission induction therapy, refer to Section “5.3.1 Dose and Regimen.”

DLT assessment at each level will first be conducted in 3 patients (including at least 1 patient of  $< 60$  years old at the time of registration in the study). DLT assessment for each patient will basically be conducted after the end of the DLT assessment period for the patient; however, if both the investigator and the sponsor decide it necessary to terminate the patient’s participation in the study, eg,  $\geq$  Grade 3 non-hematological toxicity occurs during the DLT assessment period and is assessed to be “related” to quizartinib, and premature termination of the study is considered necessary to ensure the patient’s safety, it is allowed to assess DLTs before the end of the DLT assessment period. If DLTs do not occur in the first 3 patients at Level 1, the treatment will proceed to Level 2. If DLTs occur in the first 3 patients at Level 1, an additional 3 patients will be enrolled at Level 1 or quizartinib dose escalation will be discontinued in accordance with “Table 5.4-1 Criteria for Proceeding to Level 2.” If the treatment proceeds to Level 2, the MTD will be determined in accordance with “Table 5.4-2 Criteria for Assessing Maximum Tolerated Doses (MTDs) at Level 2.”

Table 5.4-1 Criteria for Proceeding to Level 2

Incidence of DLTs in the first 3 patients at Level 1, and the decision	Incidence of DLTs when 3 patients are additionally enrolled at Level 1 (a total of 6 patients), and the decision
0 of 3 patients: Proceed to Level 2.	—
1 of 3 patients: Additionally enroll 3 patients at Level 1.	1 of 6 patients or 2 of 6 patients: Proceed to Level 2. 3 of 6 patients or 4 of 6 patients: Stop increasing the dose of quizartinib (study termination).
2 of 3 patients or 3 of 3 patients: Stop increasing the dose of quizartinib (study termination).	—

